3.1.5. Safety Analysis Set

The Safety Analysis Set includes all subjects who took at least 1 dose of Run-in SEL. This is the primary analysis set for safety analyses.

CCI

[REDACTED]

[REDACTED]

[REDACTED]

[REDACTED]

CCI

[REDACTED]

[REDACTED]

[REDACTED]

CCI

[REDACTED]

3.2. Subject Grouping

For analyses based on the Full Analysis Set, subjects will be grouped according to the treatment to which they were randomized. For analyses based on the PP Analysis Set, subjects will be grouped according to the actual treatment received in the Randomization phase. For exposure-adjusted incidence rate (EAIR) analyses based on the Safety Analysis Set, subjects and events will be grouped according to exposure (SEL or placebo). Please refer to Section 7 for details on EAIR analyses. The actual treatment received will differ from the randomized treatment only when their actual treatment differs from randomized treatment for the entire treatment duration.

For the PK Analysis Set, subjects will be grouped according to the actual treatment they received.

3.3. Strata and Covariates

Subjects will be randomly assigned to treatment groups via the interactive voice or web response system (IXRS) in a 1:1 ratio using a stratified randomization schedule. Stratification will be based on the following variables:

- eGFR_{cr} Strata:

eGFR _{cr} (mL/min/1.73 m ²)
≥ 45
≥ 30 to < 45
≥ 15 to < 30

- Albuminuria Strata: UACR < 1500 mg/g vs. ≥ 1500 mg/g
- Concomitant SGLT-2 Inhibitor Use Strata: Yes vs. No

Randomization will be stratified by the average eGFR_{cr} values from Visit A and Visit B; the average values of UACR from Visit A and Visit B; and concomitant use of SGLT-2 inhibitors assessed at Visit 1. Visit A and B values for eGFR_{cr} and Albuminuria will be transferred directly from the central laboratory to the IXRS for stratification but eGFR_{cr} values will not be released to sites, investigators, or the sponsor.

If there are discrepancies in stratification factor values between the IXRS and the clinical database, the values recorded in the clinical database will be used for analyses. Additionally, stratification discrepancies will be reviewed and assessed. Based on the assessment of stratification discrepancies, a sensitivity analysis of the primary endpoint may be performed.

3.4. Examination of Subject Subgroups

Subgroup analyses based on the following Baseline characteristics will be performed for primary and secondary endpoints:

- Age (< 65 years and ≥ 65 years)
- Sex (male and female)
- Race (white and all other races)
- Ethnicity (Hispanic and non-Hispanic)
- Pre-run-in eGFR_{cr} (mL/min/1.73m²) stratum (≥45, ≥ 30 to < 45, and ≥ 15 to < 30)
- Pre-run-in eGFR_{cr} (mL/min/1.73m²) and UACR (mg/g) stratum (45 ≤ eGFR_{cr} < 60 and 600 ≤ UACR < 5000, 30 ≤ eGFR_{cr} < 45 and 300 ≤ UACR < 5000, 15 ≤ eGFR_{cr} < 30 and 150 ≤ UACR < 5000)
- SGLT-2i use at Randomization (yes and no)
- Glucagon-like peptide-1 receptor agonist (GLP1-RA) use at Randomization (yes and no)
- Pre-run-in Baseline UACR categories (< 1500 mg/g and ≥ 1500 mg/g)
- ACEi or ARB use at Randomization (yes)
- Baseline N-terminal pro-B-type natriuretic peptide (Nt-proBNP) categories (Normal and High Normal)
- Day 1 soluble tumour necrosis factor receptor-1 (sTNFR1) subgroups (≤ 4.3 ng/mL and > 4.3 ng/mL)

3.5. Multiple Comparisons

The study has 1 primary efficacy endpoint: eGFR_{cr} slope from treatment-specific Baselines. The primary endpoint and each secondary endpoint will be evaluated at a 1-sided Type 1 error level of 0.15. No formal multiplicity adjustment will be performed. All other efficacy endpoints will also be tested using 1-sided tests at the 0.15 significance level without multiplicity adjustment.

3.6. Missing Data and Outliers

3.6.1. Missing Data

In general, missing data will not be imputed unless methods for handling missing data are specified. Exceptions are presented in this document.

For missing last dosing date of study drug, imputation rules are described in Section 4.2.1. The handling of missing or incomplete dates for AE onset is described in Section 7.1.5.2, and for prior and concomitant medications in Section 7.4.

3.6.2. Outliers

Outliers will be identified during the data management and data analysis process, but no sensitivity analyses will be conducted. All data will be included in the data analysis.

3.7. Data Handling Conventions and Transformations

The following conventions will be used for the imputation of date of birth when it is partially missing or not collected:

- If only month and year of birth is collected, then “15” will be imputed as the day of birth
- If only year of birth is collected, then “01 July” will be imputed as the day and month of birth
- If year of birth is missing, then date of birth will not be imputed.

In general, age collected at Randomization (in years) will be used for analyses and presented in listings. If age at Randomization is not available for a subject, then age derived based on date of birth and the Randomization visit date will be used instead. If an enrolled subject was not randomized, age collected at Enrollment will be used. For screen failures, the date the first informed consent was signed will be used for the age derivation. Age required for longitudinal and temporal calculations and analyses (e.g., estimates of creatinine clearance, age at date of AE) will be based on age derived from date of birth and the date of the measurement or event, unless otherwise specified.

Non-PK data that are continuous in nature but are less than the lower limit of quantitation (LOQ) or above the upper LOQ will be imputed as follows:

- A value that is 1 unit less than the LOQ will be used to calculate descriptive statistics if the datum is reported in the form of “< x” (where x is considered the LOQ). For example, if the values are reported as < 50 and < 5.0, values of 49 and 4.9, respectively, will be used to calculate summary statistics. An exception to this rule is any value reported as < 1 or < 0.1, etc. For values reported as < 1 or < 0.1, a value of 0.9 or 0.09, respectively, will be used to calculate summary statistics.
- A value that is 1 unit above the LOQ will be used to calculate descriptive statistics if the datum is reported in the form of “> x” (where x is considered the LOQ). Values with decimal points will follow the same logic as above.
- The LOQ will be used to calculate descriptive statistics if the datum is reported in the form of “≤ x” or “≥ x” (where x is considered the LOQ).

If methods based on the assumption that the data are normally distributed are not adequate, analyses may be performed on transformed data or nonparametric analysis methods may be used, as appropriate.

Sparse PK concentration values that are below the limit of quantitation (BLQ) will be presented as “BLQ” in the data listing.

Natural logarithm transformation will be used for analyzing concentrations and PK parameters in intensive PK samples. Concentration values that are BLQ will be presented as “BLQ” in the concentration data listing. Values that are BLQ will be treated as 0 at predose time points, and one-half the value of the LOQ at postdose time points for summary purposes.

The following conventions will be used for the presentation of summary and order statistics for intensive PK concentrations:

- If at least 1 subject has a concentration value of BLQ for the time point, the minimum value will be displayed as “BLQ.”
- If more than 25% of the subjects have a concentration data value of BLQ for a given time point, the minimum and Q1 values will be displayed as “BLQ.”
- If more than 50% of the subjects have a concentration data value of BLQ for a given time point, the minimum, Q1, and median values will be displayed as “BLQ.”
- If more than 75% of the subjects have a concentration data value of BLQ for a given time point, the minimum, Q1, median, and Q3 values will be displayed as “BLQ.”
- If all subjects have concentration data values of BLQ for a given time point, all order statistics (minimum, Q1, median, Q3, and maximum) will be displayed as “BLQ.”

PK parameters that are BLQ will be imputed as one-half LOQ before log transformation or statistical model fitting.

3.8. Analysis Visit Windows

3.8.1. Definition of Study Day

Study Day will be calculated from the first dosing date of blinded SEL/placebo treatment and derived as follows:

- For postdose study days: Assessment Date – First Blinded SEL/placebo Dosing Date + 1
- For days prior to the first dose: Assessment Date – First Blinded SEL/placebo Dosing Date

Therefore, Study Day 1 is the day of first dose of blinded SEL/placebo administration.

3.8.2. Analysis Visit Windows

Subject visits might not occur on protocol-specified days. Therefore, for the purpose of analysis, observations will be assigned to analysis windows.

3.8.2.1. Analysis Visit Windows for the Run-in Phase

The analysis windows for the Run-in phase will be defined based on nominal visit date, as detailed in [Table 3-1](#).

Table 3-1. Analysis Visit Windows for Visits in the Run-in Phase

Nominal Visit	Analysis Visit Window Definition	
	Lower Limit	Upper Limit
Visit A	None	Earlier of (Nominal Visit B date – 4, Run-in SEL first dosing date – 1)
Visit B	Earlier of (Nominal Visit B date – 3, Run-in SEL first dosing date)	Run-in SEL first dosing date
Visit C	Run-in SEL first dosing date + 1	For randomized subjects: Earlier of (Nominal Visit C date + 5, DB SEL/placebo first dosing date – 1) For not randomized subjects: None

3.8.2.2. Analysis Visit Windows for the Randomization Phase

The analysis windows are provided in [Table 3-2](#) through [Table 3-4](#).

Table 3-2. Analysis Visit Windows for eGFR, UACR, Vital Signs, Hematology Tests, Chemistry Tests and Pregnancy Tests in the Randomization Phase

Nominal Visit	Nominal Study Day	Visit Window Study Day	
		Lower Limit	Upper Limit
Day 1	1	Earlier of (Nominal Visit C date + 6, Study Day 1)	1
Week 4	29	2	43
Week 8	57	44	71
Week 12	85	72	127
Week 24	169	128	211
Week 36	253	212	295
Week 48	337	296	379
Week 60	421	380	463
Week 72	505	464	547
Week 84	589	548	631
Week 96	673	632	715
Week 108	757	716	799
Week 120	841	800	883
Week 132	925	884	967
Week 144	1009	968	1051
Week 156	1093	1052	1135
Week 168	1177	1136	1219

For $eGFR_{cr}$ and $eGFR_{cys}$ based on the CKD-EPI creatinine 2009 and CKD-EPI cystatin C 2012 equations, the analysis visit windows will be the same as in [Table 3-2](#).

Table 3-3. Analysis Visit Windows for HbA1c in the Randomization Phase

Nominal Visit	Nominal Study Day	Visit Window Study Day	
		Lower Limit	Upper Limit
Day 1	1	Earlier of (Nominal Visit C date + 6, Study Day 1)	1
Week 24	169	2	239
Week 48	337	240	379
Week 60	421	380	463
Week 72	505	464	547
Week 84	589	548	631
Week 96	673	632	715
Week 108	757	716	799
Week 120	841	800	883
Week 132	925	884	967
Week 144	1009	968	1051
Week 156	1093	1052	1135
Week 168	1177	1136	1219

Table 3-4. Analysis Visit Windows for Insulin, Lipid, c-peptide, Nt-proBNP, cTnI, CRP, sTNFR1, Waist Circumference, ECG, KDQOL-36, KCCQ, Work Productivity and Activity Impairment, and Sit-to-Stand Tests in the Randomization Phase

Nominal Visit	Nominal Study Day	Visit Window Study Day	
		Lower Limit	Upper Limit
Day 1	1	Earlier of (Nominal Visit C date + 6, Study Day 1)	1
Week 48	337	2	None

3.8.3. Selection of Data in the Event of Multiple Records in an Analysis Visit Window

Depending on the statistical analysis method, single values may be required for each analysis window. For example, change from Baseline by visit usually requires a single value, whereas a time-to-event analysis would not require 1 value per analysis window.

If multiple valid, nonmissing measurements exist in an analysis window, records will be chosen based on the following rules if a single value is needed:

- For pre-SEL-treatment values (Visit A and Visit B):
 - In general, the last nonmissing value on or prior to the first dosing date of Run-in SEL will be selected, unless specified differently. If there are multiple records with the same time or no time recorded on the same day, the Baseline value will be the average of the measurements for continuous data, or the measurement with the lowest severity (e.g., normal will be selected over abnormal for safety electrocardiogram (ECG) findings) for categorical data.
 - For eGFR_{cr}, eGFR_{cys}, UACR (including urine albumin, urine creatinine), serum creatinine and serum cystatin C, a single value within each of the Visit A and/or Visit B analysis window will be used to calculate pre-run-in and/or post-run-in Baselines.
 - Within each analysis window, the latest record will be selected.
 - If there is more than 1 record on the selected day, the record with the latest time will be selected. If all records have the same time, or time is missing for at least one record, the average will be taken.
- For post-SEL-treatment values (Visit C, Day 1 and post-Randomization visits):
 - The record closest to the nominal day for that visit will be selected.
 - If there are 2 records that are equidistant from the nominal day, the later record will be selected.
 - If there is more than 1 record on the selected day, the record with the latest time will be selected. If all records have the same time, or time is missing for at least one record, the average will be taken.

Definition of pre-run-in Baseline: The average of the measurements at Visit A and Visit B.

Definition of post-run-in Baseline: The average of the measurements at Visit C and Day 1.

Definition of treatment-specific Baselines: For subjects in the placebo arm, Baseline is defined as pre-run-in Baseline. For subjects in the SEL arm, Baseline is defined as post-run-in Baseline.

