6.4.8. Electrocardiogram

A single 12-lead ECG will be collected at Screening, every 48 weeks, and at EOT and EOS visits. Collection of additional ECGs for routine safety monitoring at additional time points or days is at the discretion of the Investigator based on GCP.

ECGs should always be collected prior to PK (or any other blood draw) if they are to be collected at the same nominal time point. Subjects should be resting quietly and free of distraction (e.g., television, conversation) for 10 minutes prior to and during the ECG collection. Electrocardiograms will be recorded using the site's standard ECG equipment and will include ventricular rate, PR interval, QRS interval and QT interval. ECGs will be interpreted by the investigator (or qualified designee) for clinical significance and results will be entered into the eCRF.

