7.5.2. Corrected QT Intervals

The QT interval (measured in millisecond [msec]) is a measure of the time between the start of the Q wave and the end of the T wave in the heart's electrical cycle. The QT interval represents electrical depolarization and repolarization of the ventricles. The QT interval is affected by heart rate, and a number of methods have been proposed to correct QT for heart rate.

Corrected QT (QTc) intervals will be derived using Fridericia's correction (QTcF) as follows:

$$QT_{cF} = \frac{QT}{\sqrt[3]{RR}}$$

where QT is measured in msec; RR = 60/Heart Rate (beats per min [bpm]) and RR is measured in seconds

The maximum postbaseline QTcF interval values obtained during the study will be summarized within the following categories:

- > 450 msec
- > 480 msec
- > 500 msec

The maximum postbaseline change in QTcF interval values obtained during the study will also be summarized within the following categories:

- > 30 msec
- > 60 msec

QTcF and uncorrected QT values at each visit and change from Baseline at each visit will be summarized for the Safety Analysis Set by treatment group and randomization status using descriptive statistics.

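### SAP Table 3-4 runs its only post-baseline window, Week 48, from Day 2 with no upper limit, so some by-visit ECG and waist values are mislabelled and later ECGs lost (minor, descriptive tables only)

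*SAP*

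**What the plan says.** SAP Section 3.8.2.2 has three window tables for the randomization phase.

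- Table 3-2 (eGFR, UACR, vital signs, haematology, chemistry) gives "Week 48 337 296 379": nominal day, lower limit, upper limit. Every later visit to Week 168 has its own row.
- Table 3-3 (HbA1c) gives "Week 48 337 240 379", again with later rows.
- Table 3-4 covers "Analysis Visit Windows for Insulin, Lipid, c-peptide, Nt-proBNP, cTnI, CRP, sTNFR1, Waist Circumference, ECG", three questionnaires and the sit-to-stand test. After Day 1 it has one row: "Week 48 337 2 None".

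Where a single value is needed, SAP Section 3.8.3 says: "The record closest to the nominal day for that visit will be selected". For ties: "If there are 2 records that are equidistant from the nominal day, the later record will be selected". No maximum distance is set.

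On collection, Protocol Section 6.4.8 says: "A single 12-lead ECG will be collected at Screening, every 48 weeks, and at EOT and EOS visits". On reporting, SAP Section 7.5.2 says: "QTcF and uncorrected QT values at each visit and change from Baseline at each visit will be summarized". SAP Sections 7.5, 7.5.1 and 7.5.3 promise ECG assessments at each scheduled time point, shift tables at each postbaseline visit, and interval values by visit.

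**The concern.** A window open from Day 2 onward, combined with a nearest-record rule that has no distance limit, fills the Week 48 cell with whatever post-baseline record exists. For a subject who leaves early or misses Week 48, that works as an undeclared carry-forward (or carry-back), although SAP Section 3.6.1 says missing data are not imputed unless a method is given. The by-visit table would then mix exposure times under one label.

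The second problem runs the other way. ECGs are planned every 48 weeks and Table 3-2 foresees follow-up to Week 168, yet no ECG row exists beyond Week 48. The SAP promises by-visit ECG results that its own windows cannot produce. What is at stake is the reading of the Week 48 QTcF change and the loss of later by-visit ECG data.

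**Working it through.** **Nominal days.** 48 × 7 + 1 = 337, as in Table 3-4. Likewise 96 × 7 + 1 = 673 and 144 × 7 + 1 = 1009, matching Table 3-2.

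**Which measures have a scheduled record away from Week 48** (Protocol Section 6.4.8 and Appendix 2):

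- ECG: EOT, EOS and every 48 weeks. The Appendix 2 table marks ECG at Week 48 and leaves the repeating 12-week column blank, so the Week 96 ECG rests on Section 6.4.8.
- Waist circumference: Week 48 and EOT.
- Insulin, lipids, c-peptide, Nt-proBNP, cTnI and CRP: Week 48 only after randomization, with nothing at EOT, the 30-day EOT follow-up or EOS.
- Blood biomarkers: Weeks 4, 24 and 48, EOT, 30-day EOT follow-up and EOS. The documents do not say that sTNFR1 is one of them.

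**When an early EOT ECG is required.** It is waived if an ECG was done in the previous 24 weeks (168 days). The screening ECG is at most 30 days before Visit A. The run-in windows add 7-14, 21-28 and 7-14 days, that is 35-56 days. The screening ECG is therefore 35 to 86 days old at Visit 1. Taking Day 1 as Visit 1, its age on Day d is (35 to 86) + d − 1. Setting this to 168 gives d = 168 − 86 + 1 = 83 at the earliest and 168 − 35 + 1 = 134 at the latest. EOT ECGs are thus required from roughly Day 83-134 onward. Waist circumference has no such waiver.

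**The nearest-record rule applied to Table 3-4:**

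| Records on file (Study Day) | Labelled Week 48 | Distance from Day 337 |
|---|---|---|
| 337 and 673 | 337 | 0; Week 96 record unused |
| 379 and 673 | 379 | 42 days (6.0 weeks) late; Week 96 record unused |
| 200 only (e.g. EOT ECG) | 200 | 137 days (19.6 weeks) early |
| 60 only (e.g. EOT waist) | 60 | 277 days (39.6 weeks) early |
| 673 only | 673 | 336 days (48.0 weeks) late |
| 2 and 673 | 2 | 335 days (47.9 weeks) early |

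A Week 96 ECG on its nominal day is called Week 48 only if no record exists from Day 2 to Day 672. Otherwise it has no row and is dropped.

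**Effect of bounding Week 48 at Days 296-379.** Records inside lie at most 42 days from Day 337 (379 − 337 = 42; 337 − 296 = 41). Records outside lie at least 42 days away (337 − 295 = 42; 380 − 337 = 43). The only possible tie, Day 295 against Day 379, goes to the later record, which is inside. A subject with an in-window record therefore keeps exactly the same value. Only subjects without one are affected.

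**The case against.** The case for leaving the table alone has real force.

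- The nearest-record rule protects every subject who has a true Week 48 record. This stands.
- Starting the first scheduled post-baseline visit at Day 2 is the SAP's convention: Week 4 in Table 3-2 and Week 24 in Table 3-3 do the same. For the six laboratory tests drawn only at Week 48 the open window is harmless, apart from unscheduled samples. This stands for those tests, but not for ECG and waist circumference, which have EOT collections.
- A very early EOT ECG, say at Day 40, would be waived. This stands up to about Day 83.
- The maximum-postbaseline QTcF categories do not use windows, and ECG listings show all results. This stands.
- Subjects who stop drug are asked to keep attending, so many will have a Week 48 visit. This stands for waist circumference. For ECG it helps less: SAP Section 7 ends safety summaries at last dose plus 30 days. If that cut is applied before the record is chosen, a Day 337 ECG counts only when the last dose is on Day 307 or later (337 − 30), and an earlier EOT ECG would still take the label. The SAP does not state the order.
- No unredacted SAP section names a waist summary, so the waist mislabelling matters only if one is produced.

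A reader might infer that early, off-drug and Week 96 values are generally reported as Week 48, or that the sTNFR1 comparison is diluted and its Week 4 and Week 24 course lost. The documents do not support this. A true Week 48 record always wins, and Week 96 ECGs are normally dropped rather than relabelled. The 30-day follow-up includes neither ECG nor waist circumference. The only visible sTNFR1 use is a Day 1 subgroup; anything further depends on sTNFR1 being a blood biomarker and on redacted analyses.

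**Conclusion.** The point holds in a narrow form and is minor. As written, Table 3-4 labels an early EOT or EOS ECG, an EOT waist value or, rarely, a much later ECG as Week 48 when a subject has no record near Day 337. It also leaves Week 96 and later ECGs without a by-visit row that SAP Sections 7.5 to 7.5.3 need. The damage is confined to descriptive by-visit tables. No visible primary or secondary endpoint uses Table 3-4, since eGFR follows Table 3-2.

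The number of affected subjects cannot be derived. A reader might apply the planned 15% dropout, or the 28.9% who stopped SEL 18 mg in the earlier Phase 2 study, to 300 subjects (45 to 87 subjects). The reader might then halve those shares to claim that a Week 48 difference shrinks by about 7% to 14%. That is not supported. Dropout and drug discontinuation are not counts of missing Week 48 records. An affected subject must also have another post-baseline record. The halving further assumes evenly spread stops and an effect that builds linearly, and neither is documented.

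The conclusion assumes that Day 1 coincides with Visit 1 and that ECGs are repeated every 48 weeks as Protocol Section 6.4.8 states.

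**What to change.** Amend SAP Table 3-4 for measures with EOT, EOS or later scheduled collections:

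- Bound Week 48 at Days 296-379, as in Table 3-2.
- For ECG, add Week 96 (Days 632-715) and Week 144 (Days 968-1051), also from Table 3-2.
- Report EOT and EOS records that fall outside a window under their own label.
- If sTNFR1 is drawn with the blood biomarkers, say so and give it Week 4 and Week 24 windows as well.

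The six laboratory tests collected only at Week 48 need no change.

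The cost is a table edit. The price is a smaller Week 48 row, which loses exactly the subjects without an in-window record; everyone else keeps the same value. If the SAP is already final, SAP Section 1 requires the change to be documented in the clinical study report.
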